**VENTILATOR-INDUCED LUNG VORTEX IN
PATIENTS WITH SARS-CoV-2**

NCT04174313

MARCH 25, 2020

Materials and method

This study was conducted in the ICU dedicated to COVID-19 patients of an intensive care unit at a university hospital in Argentina. Approval was obtained from local institutional review board (resolution number: 68/2019) and informed consent followed the ethical committee's recommendations.

Inclusion criteria: This single-center prospective observational study evaluated consecutively admitted adult patients who were suffering from ARDS secondary to COVID-19 and needed volume-controlled ventilation (VCV) for at least 7 days. These eligibility criteria were decided in order to allow a minimum monitoring of the mechanical variables. Those who did not meet such requirement were excluded.

ARDS was defined according to the Berlin criteria (19) while the diagnosis of COVID-19 pneumonia was established based on CT images showing such condition and on real-time polymerase chain reaction (RT-PCR) test for coronavirus disease-2019.

Exclusion criteria: Patients with do-not-resuscitate (DNR) orders and pregnant women. Cardiac arrest before ICU admission. Extra corporeal membrane oxygenation (ECMO) requirement within the first 24 h of ICU admission and chronic obstructive pulmonary disease with gold class 3 or 4, or home oxygen therapy (20).

Procedure: Patients were administered sedatives and analgesics (propofol and fentanyl) to obtain a score of -5 on the RASS scale. The protective ventilatory strategy included: low tidal volume ventilation (6 ml/kg/PBW), plateau pressure limitation (Pplat: <30 cmH₂O) and prone positioning for severe hypoxemia (21). FiO₂ and PaCO₂ were adjusted to achieve SaO₂ between 92 and 96% and pH >7.20, respectively. PEEP was titrated according to the best compliance of the respiratory system (CRS), without exceeding the Pplat limit set. Neuromuscular blockers were administered to patients suffering from severe ARDS (PaO₂/FiO₂ <100) and to the ones with hypoxemia associated with asynchronies despite the administration of sedoanalgesia, Pplat >32 cmH₂O or that needed prone positioning to improve oxygenation.

Mechanical variables and PaO₂/FiO₂ were registered daily for 14 days or until initiating assisted ventilation. These data were obtained in passive mechanical conditions.

Ventilator-induced lung injury vortex was defined as a progressive increase in driving pressure (ΔP) as Vt remained constant or even decreased.

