Refractory hypoxemia was defined as PaO₂/FiO₂ <100 despite the optimization of mechanical ventilation and prone positioning.

Respiratory mechanics: Peak airway pressure, plateau pressure, and total PEEP were measured. The value of driving pressure (ΔP : Pplat - PEEP total), static compliance of the respiratory system (CRS = Vt/ ΔP) and specific mechanical power (SMP: mechanical power/CRS) were calculated. Mechanical power was computed as: Peak airway pressure x Vt - (ΔP x Vt/2) x respiratory rate x 0.098 (13).

Complications: The following variables and complications were also observed during the period of analysis: incidence of pneumonia associated with mechanical ventilation (14), need for noradrenaline over 0.1 μ g/kg/min for more than 24 h, positive blood cultures, accumulated fluid balance, dialysis treatment, clinical and/or

echocardiographic evidence of heart failure, lactate ≥ 2 mmol/L in at least two consecutive samples, presence of persistent fever ($\geq 38^\circ$ at least once a day for three consecutive days), and the highest value of ferritin, D-dimer, C-reactive protein, troponin I and LDH obtained during the first 14 days of invasive mechanical ventilation.

Statistical analysis: Dichotomic data are reported as frequencies and percentages while continuous data are presented as mean (standard deviation) or median (interquartile range) as appropriate, depending on the normality of distribution. Kolmogorov–Smirnov test was used to test normality of distribution for continuous variables. Comparisons between the two groups (VILI vortex vs. No VILI vortex) and intragroup (day: 7 vs. day: 14) were analyzed by either an independent t-test or the Mann–Whitney test. Differences in categorical variables were assessed using the χ^2 or Fisher's exact test.

The mortality predictive model following refractory hypoxemia as well as mortality for any reason was analyzed on day 90 by means of ROC curves. Survival difference between both groups was analyzed through longrank test. Cox's proportional hazards regression test was used to study the relationship between VILI vortex intensity and accumulative risk of death from refractory hypoxia. The difference of driving pressure ($\Delta\Delta P$) between days 7 and 14 was regarded as VILI vortex intensity expression. That was the period in which we more frequently observed VILI vortex development.

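### The within-group day 7 versus day 14 comparison uses tests for independent samples on repeated measurements from the same patients; it needs a paired analysis

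*Combined protocol and SAP*

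**What the plan says.** The Statistical analysis section assigns one pair of tests to two different comparisons. The first is vortex versus no vortex. The second is the change over time within each group: "intragroup (day: 7 vs. day: 14) were analyzed by either an independent t-test or the Mann–Whitney test". A Kolmogorov–Smirnov test on the continuous variables checks normality; differences between days are not mentioned.

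The Procedure paragraph says that the mechanical variables and PaO₂/FiO₂ "were registered daily for 14 days or until initiating assisted ventilation". Eligibility is limited to patients who "needed volume-controlled ventilation (VCV) for at least 7 days".

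The plan already links the two days patient by patient elsewhere. The change in driving pressure "between days 7 and 14 was regarded as VILI vortex intensity expression" and is the exposure in the Cox model, which requires a difference for each patient.

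Neither a paired t-test, a signed-rank test, repeated-measures ANOVA nor a mixed model is named in the document. It also does not say how many patients have values on both days.

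**The concern.** The independent t-test and the Mann–Whitney test both assume that the two sets of values come from different people. Here every patient with a day-14 value should also have a day-7 value, since eligibility required 7 days of controlled ventilation. The two values share that patient's lung condition, body size and ventilator settings, so they should be positively correlated. An unpaired test leaves that shared variation in the error term.

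The likely result is a p-value that is too large and an interval that is too wide. A real within-group change, for example in PaO₂/FiO₂, could be missed and reported as no change. The study is about how lung mechanics evolve over this period, so such a statement would carry some weight with readers, even though the comparison is a supporting one.

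**Working it through.** **Inputs.** From the documents: the test, the daily recording and the 0.05 threshold (two-sided assumed). The documents give no sample size, SD, correlation or target change, so there is no figure to reproduce. Assumed: bivariate normal values, equal SDs on both days, and within-patient correlation ρ of 0.3, 0.5 or 0.7. Triplets below follow that order.

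**1. Standard error with n complete pairs.** The unpaired test uses variance 2σ²/n for the mean difference. The true variance is 2σ²(1 − ρ)/n. The standard error is therefore too large by 1/√(1 − ρ):
- 1/√0.7 = 1.20
- 1/√0.5 = 1.41
- 1/√0.3 = 1.83

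**2. Actual type I error at nominal 5%.** In large samples this is 2[1 − Φ(1.96/√(1 − ρ))], which gives 1.9%, 0.6%, 0.03%. Simulation with 30 pairs gives 2.2%, 0.6%, 0.1% for the independent t-test, 2.1%, 0.6%, 0.15% for Mann–Whitney, and about 5% for the paired t-test.

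**3. Power for a 0.6 SD change, complete pairs (simulated).**

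| Pairs | Independent t-test | Paired t-test |
|---|---|---|
| 10 | 21%, 18%, 15% | 30%, 39%, 59% |
| 20 | 45%, 44%, 43% | 58%, 72%, 91% |
| 30 | 65%, 68%, 72% | 77%, 89%, 98% |

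At ρ = 0 pairing gains nothing (20 pairs: 46% independent, 44% paired).

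**4. Some patients without day 14.** Suppose 30 patients at day 7 and 18 at day 14. Three analyses are compared: the current independent t-test (30 against 18), the paired t-test on the 18 completers, and a two-day model. The model estimates the day-14 mean as the completers' day-14 mean plus b × (day-7 mean of all 30 − day-7 mean of the 18), where b is the slope of day 14 on day 7 among completers. It then subtracts the day-7 mean of all 30. Its variance is s²[1/18 + (difference of day-7 means)²/Sxx] + (b − 1)²s₇²/30, where s² is the residual variance, Sxx the completers' day-7 sum of squares and s₇² the day-7 variance. The t reference has 16 df.

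| 12 of 30 leave | Current | Paired completers | Two-day model |
|---|---|---|---|
| At random: power, 0.6 SD change | 50%, 51%, 51% | 52%, 67%, 87% | 56%, 70%, 88% |
| At random: type I error | 2.7%, 1.5%, 0.5% | 5.0% | 4.4% |
| Lowest day-7 value plus standard logistic noise: type I error | about 3.5% | 12–13%, 10%, 8% | about 4% |
| Exactly the 12 lowest day-7 values (extreme): type I error | 6.5%, 12%, 24% | 39%, 28%, 18% | about 4% |

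In the extreme case at ρ = 0.3, the bias in SD units is +0.19 (current), −0.44 (paired completers) and 0.00 (model). With only 2 or 3 of 30 leaving in the gradual way, the paired test rejects about 5 to 6% under no change.

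**The case against.** The strongest objection is that the obvious repair can be worse than the fault. Recording stops when assisted ventilation starts, a transition plausibly related to lung condition, and patients may also die before day 14. If leaving depends gradually on the day-7 value and 12 of 30 leave, the completers-only paired test rejects a true null in 8 to 13% of samples, while the present test stays near 3.5%. This stands. It argues against a bare paired test when many day-14 values are missing. It does not justify a test that ignores the pairing, which itself reaches 24% in the extreme case. The two-day model held about 4% in every departure pattern tried.

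Two further points limit the weight of the finding:
- With positive correlation and random departure the error costs power and does not create false positives. A negative correlation would reverse this (ρ = −0.3 gives 8.6%), but that is implausible for repeated lung mechanics in one patient.
- The "vortex was defined as a progressive increase in driving pressure", so the groups are formed by the change being tested, although the definition names no particular days. For driving pressure, and for compliance and "specific mechanical power (SMP: mechanical power/CRS" derived from it, within-group p-values mean little under any test. Plateau pressure and mechanical power are also arithmetically tied to driving pressure. The change in PaO₂/FiO₂ is not built in by definition in this way.

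The text may simply be loosely worded and paired tests may have been run. In that case the method is misdescribed and the sentence still needs correcting.

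**Conclusion.** The concern holds. The stated test does not match the design for the within-group comparison, and nothing else in the document supplies a suitable method. If correlation is positive and day-14 values are missing at random, the cost is lost power and precision. With 20 complete pairs and a 0.6 SD change, the shortfall is 13, 28 or 48 percentage points at ρ of 0.3, 0.5 or 0.7 (58 − 45, 72 − 44, 91 − 43). If leaving depends on the day-7 value, even the conservative direction is not assured. All sizes rest on assumed inputs; the mismatch itself does not.

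The reach is limited. Using these tests for vortex versus no vortex raises no pairing problem, and the ROC, log-rank and Cox analyses do not use them. This should be fixed, but it does not threaten the main analyses.

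**What to change.** - For day 7 versus day 14 within a group, replace the independent tests with a paired t-test or Wilcoxon signed-rank test on patients with both days. Judge normality on the paired differences. Keep the independent tests for the between-group comparison.
- Report the mean or median paired difference with its 95% CI, and the numbers with day 7, with day 14 and with both. Give the reason for each missing day-14 value, separating assisted ventilation from death.
- If many patients lack day 14, use a likelihood-based repeated-measures model limited to the two days with unstructured covariance. State what counts as many before looking at the results. The simulations suggest that 2 or 3 of 30 does little harm and 12 of 30 is too many. The model can be fitted as a regression of day 14 on day 7, combined with all day-7 values.
- Avoid a random-intercept model over all daily values as a shortcut. If correlation decays with lag (AR(1) assumed, 12 of 30 leaving at random after day 7), its simulated type I error was 14 to 17%.
- State the limits. The paired test drops patients without day 14 and can be more biased than the current test if leaving depends on day 7. No method here corrects for leaving that depends on the unrecorded later course. The model's day-14 mean also includes patients no longer passively ventilated, or who have died.
- Label within-group p-values for driving pressure, compliance and specific mechanical power as descriptive; the same caution suits plateau pressure and mechanical power.

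The cost is a few sentences in the Statistical analysis section and a re-run on values already recorded. No new data are needed.

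### The log-rank test of vortex against no vortex treats as fixed a group that is settled only while patients survive on passive ventilation up to day 14, with no landmark or time-updated exposure

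*Combined protocol and SAP*

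**What the plan says.** All references are to the combined protocol and SAP.

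- **Who is included** (Inclusion criteria): adults with COVID-19 ARDS who "needed volume-controlled ventilation (VCV) for at least 7 days".
- **When the exposure can be seen** (Procedure): the mechanical variables were "registered daily for 14 days or until initiating assisted ventilation". The next sentence adds: "These data were obtained in passive mechanical conditions".
- **What the exposure is** (end of Procedure): vortex "was defined as a progressive increase in driving pressure" while tidal volume stays level or falls. No window, onset day or minimum rise is given.
- **How survival is compared** (Statistical analysis): "Survival difference between both groups was analyzed through longrank test". The groups are vortex and no vortex. No time origin, risk set or follow-up horizon is stated for this test.
- **What is tied to fixed days** (Statistical analysis): only the intensity measure ΔΔP, the difference in driving pressure that "between days 7 and 14 was regarded as VILI vortex intensity expression". On those days it remarks: "That was the period in which we more frequently observed VILI vortex development".
- **The other mortality analyses** (Statistical analysis): a Cox model relates intensity to death from refractory hypoxaemia, and the mortality prediction model "was analyzed on day 90 by means of ROC curves". Neither has a stated population or time origin.

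**The concern.** The 7-day ventilation requirement works as an implicit landmark at day 7. By the plan's own account, however, vortex appears mostly in the following week, when patients are also dying or moving to assisted ventilation. Group membership is therefore partly a result of what happens to the patient after entry.

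Two distortions follow, in opposite directions:

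- A patient who dies before a rise is visible adds an early death to the no-vortex group. To be classed as vortex, a patient must live until the rise shows. This pushes the hazard ratio below 1.
- A patient who improves and leaves passive ventilation before a rise is visible adds a good-prognosis survivor to the no-vortex group. This pushes the hazard ratio above 1.

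The documents give no rule for classifying either kind of patient. A log-rank p-value from the plan as written would mix any real association with these two artefacts. Separately, ΔΔP needs a day-14 value. If the Cox and ROC analyses use only patients who have one, their conclusions apply to patients still on controlled ventilation at day 14, and the reader is not told so.

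**Working it through.** The plan gives no sample size, event count or hazard ratio to reproduce. The structural point needs no numbers. The size can only be illustrated, and **every rate below is assumed**.

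**Set-up.** Vortex has no effect on death (true HR 1). All patients are on controlled ventilation at day 7. Each has a latent probability of 0.5 of a rise, with onset uniform over days 7–14 or, because the plan says only that days 7–14 were the more frequent period, over days 2–14. The death hazard after weaning to assisted ventilation is 0.003 per day, and follow-up ends at day 90. A rise counts as vortex only if it starts before death, weaning and day 14. Daily hazards on controlled ventilation are shown as days 7–14 / after day 14:

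| Scenario | Death | Weaning |
|---|---|---|
| S1 | 0.03 / 0.01 | 0 / 0.05 |
| S2 | 0.005 / 0.03 | 0.06 / 0.03 |
| S3 | 0.03 / 0.03 | 0.03 / 0.03 |
| S4 | 0.02 / 0.03 | 0.06 / 0.03 |

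**Step 1: who still has a day-14 value.** With λ = death + weaning hazard in days 7–14, the share is exp(−7λ):

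- S1: exp(−0.21) = 0.81
- S2: exp(−0.455) = 0.63
- S3: exp(−0.42) = 0.66
- S4: exp(−0.56) = 0.57

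Of an assumed 60 patients, that is 34 to 49.

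**Step 2: how many rises are never seen.** With onset uniform over days 7–14, the share of latent-vortex patients who leave observation first is 1 − (1 − exp(−7λ))/(7λ). This gives 10%, 20%, 18% and 23% for S1 to S4. All of these patients land in no vortex. The share of them lost through death is death hazard/λ: 100% in S1, 0.005/0.065 = 8% in S2, 50% in S3 and 0.02/0.08 = 25% in S4. That mix determines the direction of the bias.

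**Step 3: the unlandmarked comparison.** Hazard ratios come from very large simulated samples. Rejection rates come from 4,000 trials at n = 60 and 2,000 at n = 120, at a nominal 5%.

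| | S1 | S2 | S3 | S4 |
|---|---|---|---|---|
| HR, onset days 7–14 | 0.65 | 1.26 | 0.90 | 1.09 |
| Rejection, n = 60 | 18% | 10% | 5% | 6% |
| Rejection, n = 120 | 33% | 14% | 7% | 6% |
| HR, onset days 2–14 | 0.78 | 1.13 | 0.94 | 1.05 |
| Rejection, n = 60 | 10% | 7% | 5% | 6% |

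**Step 4: the alternatives, same data.**

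- Day-14 landmark in patients alive and still on controlled ventilation: HR 0.99–1.01, rejection 4–6%, in all eight runs.
- Day-14 landmark that also keeps weaned patients: HR roughly 1.1 to 1.4 in S2–S4. The restriction to controlled ventilation is therefore essential.
- Time-updated Cox from day 7 that ignores weaning: HR 1.09–1.34 in the six runs with weaning before day 14.
- The same model censored at weaning, or stratified by ventilation state: HR 1.00–1.01 in all eight runs.
- Cox limited to patients with a day-14 value: same HR whether the clock starts at day 7 or day 14. Nobody in that set can die before day 14, so the risk sets are identical.

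**Step 5: a second null model with different assumptions.** This used N = 100, 50% dead by day 90, a 40% risk of vortex over days 7–14 and no weaning. With 10%, 25% and 40% of deaths in days 7–14, the ever-vortex log-rank gave HRs of 0.93, 0.81 and 0.74, with rejection of 5.9%, 10.1% and 16.4%. Once weaning was added, a landmark that kept weaned patients gave HRs of 1.14 to 1.46, consistent with step 4.

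**The case against.** **The groups may already be day-14 completers.** The within-group comparison of day 7 with day 14 needs day-14 values. If the log-rank groups were limited in the same way, the test would already be conditional on day 14 and only a reporting gap would remain. The documents do not say this: only ΔΔP and the day-7 against day-14 comparison need a day-14 value, and the vortex definition does not. The plan leaves the choice open, and under its plainest reading, a split of all eligible patients, an unseen rise becomes no vortex.

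**The bias is modest in most scenarios.** This stands as a description. At n = 60, four of the eight runs reject at 5–6%. The largest figure comes from S1, which assumes no weaning in days 7–14 and a death hazard three times higher then than later. In S3 and S4, however, the near-nominal rates reflect two biases partly cancelling, and nothing in the documents assures that they would.

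**The plan is observational and does not claim an effect.** True, but the distortion affects the association as well: the simulated groups differ although vortex is unrelated to death.

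**The remedy rests on assumptions too.** This stands in part. In a scenario where severity drives both death and weaning, and vortex itself delays weaning, the landmark HR was 1.19–1.32, and censoring at weaning gave 0.81–0.85. That is not a clean null, since vortex there prolongs exposure to the higher hazard on controlled ventilation. It does show that censoring at weaning assumes weaning is uninformative, and that a landmark result is still an unadjusted association.

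**Landmark as the main analysis is a preference.** Fair: the stratified time-updated model did equally well in these runs and uses all eligible patients. The landmark has the merit of keeping the plan's chosen test.

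**Conclusion.** The concern holds. The log-rank comparison has no time origin, landmark or time-updated exposure. Its grouping depends on survival and ventilation status during the days when vortex mostly develops. This is more than missing detail, because following the plan as written can give a biased survival comparison.

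Confidence in the structural point is high. The size is illustrative only: null hazard ratios of 0.65 to 1.26, and rejection of 5% to 18% at n = 60 (up to 33% at n = 120), under assumed death, weaning and vortex rates. The net direction cannot be determined from the documents. For the ΔΔP Cox and ROC analyses the finding is narrower. If they use only patients with a day-14 value, they are already conditional on reaching day 14 on controlled ventilation, and the fault is that this population is not stated.

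**What to change.** 1. Run the log-rank comparison from a day-14 landmark, in patients alive, still on controlled ventilation and with a day-14 driving pressure. Assign the group from records up to day 14.
2. State the same population and time origin for the ΔΔP Cox and ROC analyses.
3. Report deaths and moves to assisted ventilation in days 7–14 separately, by last observed driving-pressure trend, so that the excluded patients are visible.
4. As a sensitivity analysis in all eligible patients, run Cox from day 7 with vortex (or driving pressure minus its day-7 value) as a time-updated covariate. Treat assisted ventilation as a time-varying state or stratum, or censor at its start and state the assumption that this censoring is uninformative. A model that ignores assisted ventilation remains biased.

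The cost is SAP wording and a re-run on daily records already taken. The landmark set is smaller (57–81% of eligible patients under the assumed rates), it omits deaths in days 7–14, and its conclusion applies only to patients still on controlled ventilation at day 14.

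### Survival with and without the vortex is compared without adjustment, so any difference may partly reflect day-7 respiratory severity, by an amount and in a direction the documents cannot settle

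*Combined protocol and SAP*

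**What the plan says.** All references are to the combined protocol and SAP, Materials and method.

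- **Design (Inclusion criteria).** "This single-center prospective observational study evaluated consecutively admitted adult patients". Entry is restricted to those who "needed volume-controlled ventilation (VCV) for at least 7 days".
- **Groups (Procedure).** The vortex is "defined as a progressive increase in driving pressure (ΔP) as Vt remained constant or even decreased". No numeric threshold and no start day are given.
- **Data (Procedure).** Mechanical variables and PaO2/FiO2 are "registered daily for 14 days or until initiating assisted ventilation".
- **Group survival analysis (Statistical analysis).** "Survival difference between both groups was analyzed through longrank test".
- **Regression (Statistical analysis).** "Cox's proportional hazards regression test was used to study the relationship between VILI vortex intensity and accumulative risk of death from refractory hypoxia". Intensity is ΔΔP, the difference in driving pressure (ΔP) between days 7 and 14. No adjustment variable is named.

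The t, Mann–Whitney, χ² and Fisher tests in the same section can display a group imbalance but do not remove it. No sample size, event count, mortality rate or hazard ratio is stated.

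**The concern.** Patients enter the vortex group because of how their lungs behave. Whatever drives that behaviour may also drive death, and a log-rank test without strata attributes the whole survival difference to group membership.

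The plan itself gives reason to think day-7 oxygenation matters. Under Procedure, a PaO2/FiO2 below 100 marks severe ARDS. The definition of refractory hypoxemia uses the same boundary, and death from that cause is the outcome of the Cox model. A patient with a low ratio on day 7 therefore starts closer to that outcome by definition. If such patients are unevenly spread between the groups, neither the log-rank p-value nor the ΔΔP hazard ratio can be separated from day-7 respiratory severity.

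**Working it through.** **Availability of day-7 values.** Entry needs at least 7 days of volume-controlled ventilation, and recording is daily until day 14 or assisted ventilation. Day-7 mechanics and PaO2/FiO2 should therefore exist for essentially all enrolled patients. Lactate and noradrenaline need are described over the whole period, and the laboratory markers as 14-day peaks. So day-7 severity is supported for respiratory measures only, not for systemic illness.

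**Size of the possible bias.** The plan gives no figure to reproduce, so every input here is an assumption. Let h be the hazard ratio for death of a binary day-7 severity marker, p1 and p0 its prevalence in vortex and no-vortex patients, and let the true vortex HR be 1. At the start of follow-up:

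apparent HR ≈ [1 + (h − 1)p1] / [1 + (h − 1)p0]

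For example, h = 2 with 60% vs 30% gives 1.6/1.3 = 1.23. With h = 3 and 70% vs 30% it gives 2.4/1.6 = 1.50. Reversing the latter gives 1.6/2.4 = 0.67.

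A simulation extends this to follow-up from day 14 to day 90. It assumed 40% of patients with vortex, 30% mortality in non-severe patients over that period, two-sided 0.05 and 3,000 runs per scenario.

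| h | p1 / p0 | Formula HR | Simulated HR | Plain log-rank rejections, N = 60 / 100 / 200 |
|---|---|---|---|---|
| 1.5 to 3 | 50/50 | 1.00 | 1.00–1.02 | 4.6–5.4% throughout |
| 1.5 | 60/40 | 1.08 | 1.09–1.10 | 5.2 / 6.2 / 7.0% |
| 2 | 60/40 | 1.14 | 1.15–1.17 | 7.6 / 6.7 / 10.1% |
| 3 | 60/40 | 1.22 | 1.25 | 9.2 / 10.9 / 19.8% |
| 1.5 | 70/30 | 1.17 | 1.18–1.20 | 7.6 / 8.1 / 11.1% |
| 2 | 70/30 | 1.31 | 1.33–1.35 | 10.6 / 13.9 / 23.4% |
| 3 | 70/30 | 1.50 | 1.56–1.57 | 20.1 / 30.9 / 52.6% |
| 1.5 | 30/70 | 0.85 | 0.86 | 6.0 / 6.3 / 10.9% |
| 2 | 30/70 | 0.76 | 0.76–0.78 | 9.2 / 13.5 / 22.7% |
| 3 | 30/70 | 0.67 | 0.67 | 18.8 / 28.0 / 50.9% |

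The simulated HR is a one-step log-rank estimate over the whole follow-up, so it need not equal the start-of-follow-up formula. Stratifying the log-rank test by the marker gave 4.4–5.9% rejections in every scenario. The simulation standard error at 5% is √(0.05 × 0.95/3,000) = 0.4 percentage points.

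**Direction for driving pressure.** If ΔP on days 7 and 14 has equal variance and correlation ρ, the day-7 level and the later change correlate at −√[(1 − ρ)/2]. This is −0.59 for ρ = 0.3 and −0.22 for ρ = 0.9. A stiffer lung on day 7 does not by itself imply a larger later rise.

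**Effect of day-7 ΔP in the ΔΔP model.** With ΔΔP = D14 − D7, where D7 and D14 are ΔP on those days:

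b1·ΔΔP + b2·D7 = b1·D14 + (b2 − b1)·D7

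The ΔΔP coefficient is then the coefficient of day-14 ΔP at a given day-7 value.

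**The case against.** A reader might infer that sicker patients' excess deaths are in fact credited to the vortex. The documents do not support that. They report no group comparison, balanced severity produces no bias, and a reversed imbalance would hide a vortex effect. For ΔP, the negative correlation above makes masking at least as plausible as inflation. This removes any claim about direction, but an error of unknown sign is still a reason to adjust.

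Four further objections have weight.

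- **Purpose.** No causal objective is stated, and the wording about a predictive model and a relationship fits prognosis. As description of prognosis, an unadjusted log-rank test is valid. What stands is that the plan does not limit its conclusions to that.
- **Event count.** It is tempting to say that two covariates are clearly affordable. Without a number of deaths this cannot be known, and the Cox outcome is narrower than all-cause death.
- **Timing of the exposure.** The vortex definition has no start day. The plan says only that days 7 to 14 were when it developed more often. For earlier onset, day-7 ΔP is part of the exposure and day-7 PaO2/FiO2 may be its consequence, so adjustment could remove a real effect. This stands, and makes the remedy conditional.
- **Pneumonia.** Ventilator-associated pneumonia before day 7 may look like a ready covariate. Complications lists only "incidence of pneumonia associated with mechanical ventilation" over the period of analysis, with no statement that onset is dated.

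**Conclusion.** The concern holds in a limited form. The groups are not randomised, their survival is compared with no adjustment, and the ΔΔP Cox model does not fill the gap. Any difference may partly reflect day-7 respiratory severity.

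The bias cannot be sized or signed from the documents. With no true effect, the assumed scenarios give apparent hazard ratios from about 0.67 to 1.57. These figures rest on severity hazard ratios of 1.5 to 3, prevalence splits up to 70/30 in either direction, and the assumed vortex share and mortality. They show what is possible, not what occurred.

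This should be changed, because the values needed are already recorded and the plan otherwise offers only a crude comparison. Forming the exposure from day 7 to 14 data raises a separate timing problem, which covariate adjustment does not repair.

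**What to change.** 1. Specify vortex onset as after day 7, so that day-7 values precede the exposure.
2. Add a Cox model for vortex versus no vortex adjusted for day-7 PaO2/FiO2 and, if the event count allows, day-7 ΔP. State in advance how that will be decided. If events are too few, use a log-rank test stratified by day-7 PaO2/FiO2 with a cut-off fixed beforehand.
3. Add the same covariates to the ΔΔP model. If day-7 ΔP is included, state that the ΔΔP coefficient equals the day-14 ΔP coefficient and interpret it that way.
4. Present the plain log-rank test and Kaplan–Meier curves as unadjusted description, and limit conclusions to association.
5. Do not adjust for pneumonia before day 7 unless onset dates are recorded.

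The cost is a few sentences in Statistical analysis, an onset rule in the vortex definition, and one added model on values already collected. The downsides are a wider interval and possible over-adjustment for patients whose vortex began before day 7.
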